### **9.3.3. Sensitivity Analyses of the Primary Efficacy Results**

The assumptions relative to the ANCOVA model (e.g. linearity, normality) specified for the primary analysis of the primary endpoint will be checked and any violations of these assumptions will be handled through non-parametric statistical methods.

A tipping point sensitivity analysis will be performed to assess the robustness of the missingness assumptions. This sensitivity analysis is based on “delta adjustments” which is a commonly used approach to assess the impact of missing data in clinical trials (O’Kelly and Ratitch, 2014). The imputed Week 24 glucocorticoid daily dose values (from the MI procedure described in Section 16.1) for subjects in either the crinecerfont treatment group or the placebo treatment group will be delta-adjusted (with a range of plausible penalties for each treatment group) until the treatment difference at Week 24 is no longer statistically significant. The implementation procedure for the tipping point analysis is described in Appendix 16.4. The combinations of delta adjustments that tip the result from statistically significant to insignificant along with the corresponding insignificant p-values will be presented in a table and may be presented in a figure.

A complete-case sensitivity analysis will also be performed to test the robustness of the multiple imputation procedure. The ANCOVA analysis for the primary endpoint will be repeated using only subjects with observed data at Week 24. Subjects who are missing the Week 24 primary endpoint will be excluded from the analysis.

Descriptive statistics and LS means for the sensitivity analyses will be presented by treatment group along with the LS-mean treatment difference, 95% confidence intervals, and nominal p-values.

#### **9.3.4. Supplementary Analyses of the Primary Efficacy Results**

The following supplementary analyses of the primary efficacy results will also be performed:

- As an alternative method to handling missing data at Week 24, the ANCOVA analysis for the primary endpoint will be repeated using the Week 20 daily glucocorticoid dose (based on the Week 20 analysis visit date for androstenedione) for subjects who are missing Week 24 glucocorticoid dose data. This analysis will follow the same conventions as are used for the primary analysis of the primary endpoint except in the case for subjects who have missing glucocorticoid dose at Week 24, their Week 20 glucocorticoid dose will be used instead. The same definition of androstenedione control will be implemented using androstenedione values at baseline and Week 20 for this subset of subjects. For subjects missing both Week 20 and Week 24 glucocorticoid doses, the missing data imputation strategy from the primary analysis of the primary endpoint will be used.
- The ANCOVA analysis for the primary endpoint will be repeated using the average of the Week 20 and Week 24 daily glucocorticoid doses. Post-glucocorticoid dose androstenedione values at Week 20 and Week 24 will be averaged and compared against the baseline post-glucocorticoid dose androstenedione value to assess whether the subject maintained androstenedione “control” (where “control” is defined as the average of the Week 20 and 24 androstenedione values  $\leq 120\%$  of baseline or  $\leq \text{ULN}$  for age and sex). If a subject is missing Week 20 or Week 24, then the visit with the observed values will be used instead of the average. Subjects who are missing Week 20 and Week 24 glucocorticoid dose data or all Week 20 and Week 24 androstenedione values will have their data imputed through the multiple imputation procedure following the same methods as described in the primary analysis of the primary endpoint.

- The ANCOVA analysis as described for the primary endpoint will be repeated using the absolute (rather than the percent) change from baseline in the glucocorticoid total daily doses (in mg/m^2/day) captured in the glucocorticoid concomitant medication eCRF at baseline and Week 24. All conventions used in the primary analysis of the primary endpoint will be used in this supplementary analysis.
- The ANCOVA analysis (as described above) for the primary endpoint will be repeated using the absolute change from baseline in glucocorticoid daily doses in mg/day (ie, not adjusted for BSA). All conventions used in the primary analysis of the primary endpoint will be used in this supplementary analysis.
- The ANCOVA analysis for the primary endpoint will be repeated using the Week 24 data without setting glucocorticoid dose reductions to 0 due to loss of androstenedione control. That is, all observed and multiply-imputed GC dose data at Week 24 will be used regardless of the subject's androstenedione values. Missing data at Week 24 will be imputed using the same methods as in the primary analysis of the primary efficacy endpoint.
- The ANCOVA analysis for the primary analysis of the primary endpoint will be repeated with a modification to the androstenedione control criteria, with androstenedione control being defined as  $\leq 150\%$  of the baseline value or  $\leq$  ULN. Missing data at Week 24 will be imputed using the same methods as in the primary analysis of this endpoint.
- The ANCOVA analysis for the primary analysis of the primary endpoint will be repeated with androstenedione control being defined as  $\leq 180\%$  of the baseline value or  $\leq$  ULN. Missing data at Week 24 will be imputed using the same methods as in the primary analysis of this endpoint.
- The ANCOVA analysis for the primary analysis of this endpoint will be repeated using the latest glucocorticoid total daily dose at Week 12, Week 16 or Week 20 where androstenedione is controlled if control is not met at Week 24. Note that missing data at Weeks 12, 16 and 20 will not be imputed. For subjects who do not meet the androstenedione control definition at any visit between Week 12 and Week 24 or are missing all data between Week 12 and Week 20, their percent change from baseline in glucocorticoid total daily dose will be set to 0. Missing data at Week 24 will be imputed using the same methods as in the primary analysis of this endpoint.
- The ANCOVA analysis for the primary analysis of this endpoint will be repeated using the highest glucocorticoid total daily dose at Week 12, Week 16 or Week 20 where androstenedione is controlled if control is not met at Week 24. Note that missing data at Weeks 12, 16 and 20 will not be imputed. For subjects who do not meet the androstenedione control definition at any visit between Week 12 and Week 24 or are missing all data between Week 12 and Week 20, their percent change from baseline in glucocorticoid total daily dose will be set to 0. Missing data at Week 24 will be imputed using the same methods as in the primary analysis of this endpoint.
- The ANCOVA analysis for the primary analysis of this endpoint will be repeated using the average of the two screening post-GC dose androstenedione visit values and the Day 1 post-GC dose androstenedione value at baseline as compared to the average of the

Week 20 and Week 24 post-GC dose androstenedione values. If the Week 20 and Week 24 total daily glucocorticoid doses are not equal, then the Week 24 post-GC dose androstenedione value will be used instead. If there is missing data (GC or androstenedione) at Week 20 or Week 24 then the observed data from the visit with non-missing data will be used instead. If both Week 20 and Week 24 have missing GC or androstenedione data then the Week 24 imputed value will be used. Missing data at Week 24 will be imputed using the same methods as in the primary analysis of this endpoint.

- The ANCOVA analysis for the primary analysis of this endpoint will be repeated using weight collected at Week 24 in the calculation of BSA (instead of using Day 1). That is, the baseline glucocorticoid total daily dose in mg/m^2/day will be calculated using height at the screening visit and baseline weight and the Week 24 glucocorticoid total daily dose in mg/m^2/day will be calculated using height at the screening visit and weight at the Week 24 visit in the calculation of Week 24 BSA. If Week 24 weight is missing, baseline BSA will be used instead. Missing data at Week 24 will be imputed using the same methods as in the primary analysis of this endpoint.

Descriptive statistics and LS means for the supplementary analyses will be presented by treatment group along with the LS-mean treatment difference, 95% confidence intervals, and nominal p-values.

## **9.4. Analysis of Key Secondary Efficacy Endpoints**

### **9.4.1. Serum Androstenedione**

The first key secondary endpoint is the change from baseline in serum androstenedione at Week 4. The pre-morning glucocorticoid dose androstenedione values at baseline and Week 4 will be used in the calculation of this endpoint (as defined in Section 6.3.4). If a subject is missing their baseline or Week 4 pre-glucocorticoid dose androstenedione value, then the post-glucocorticoid androstenedione values at baseline and Week 4 will be used instead. The primary analysis of this endpoint will be performed using an ANCOVA model as described in Section 9.2.1. Subjects who are missing all androstenedione levels at Week 4 will have their Week 4 data imputed through the multiple imputation procedure described in Section 16.2.

Statistical significance for the treatment comparison will be determined using the multiple comparison procedure described in Section 9.1. Descriptive statistics and LS means will be presented by treatment group along with the LS mean treatment difference, 95% confidence intervals, and p-value.

Descriptive statistics will be presented by treatment group and visit for the serum androstenedione observed and change from baseline values through Week 24. For visits where androstenedione is collected more than once (e.g., Day 1), each visit will be presented with the pre- and post- morning GC dose androstenedione values. The androstenedione observed values from the two screening visits and the average of these values will also be summarized.

Mean ( $\pm$ SEM) values of serum androstenedione at each visit will be summarized in line graphs by treatment group. For visits where androstenedione is collected more than once, each visit will be presented with the pre- and post- morning GC dose androstenedione values on separate plots. Similar graphs will be presented for the changes from baseline.

A tipping point sensitivity analysis of change from baseline in serum androstenedione at Week 4 will be performed to assess the robustness of the missingness assumptions as was described for the primary endpoint in Section 9.3.3. The implementation procedure for the tipping point analysis is described in Appendix 16.5 for each key secondary efficacy endpoint.

A complete-case sensitivity analysis will also be performed to test the robustness of the multiple imputation procedure. The ANCOVA analysis for change from baseline in serum androstenedione will be repeated using only subjects with observed data at Week 4. Subjects who are missing Week 4 androstenedione values will be excluded from the analysis.

As a supplementary analysis, the percent change from baseline in serum androstenedione will be analyzed using the same method as described in the primary analysis of this endpoint. Missing data will also be imputed using the same methods as described in the primary analysis of this endpoint.

As a supplementary analysis, the change from baseline to Week 4 in serum androstenedione will be analyzed using the average of the two screening post-GC dose visit values and the Day 1 post-GC dose value as compared to the Week 4 post-GC dose androstenedione value. If one or more of the screening or Day 1 values is missing or if collected pre-GC dose, then the average of the remaining values will be used instead. This analysis will be performed using an ANCOVA model as described above. Missing data will also be imputed using the same methods as described in the primary analysis of this endpoint.

As a supplementary analysis, the change from baseline to Week 4 in serum androstenedione, derived as a multiple of the ULN (calculated as observed value divided by the ULN value) [based on age and sex], will be analyzed using the same method as described in the primary analysis of this endpoint. Missing data will also be imputed using the same methods as described in the primary analysis of this endpoint.

#### **9.4.2. Physiologic Glucocorticoid Daily Dose Responder Analysis**

The second key secondary endpoint is the achievement of a reduction in glucocorticoid daily dose to physiologic levels ( $\leq 11 \text{ mg/m}^2/\text{day}$  hydrocortisone equivalent adjusted for BSA) at Week 24, while Week 24 androstenedione is adequately controlled at  $\leq 120\%$  of baseline or  $\leq \text{ULN}$  for age and sex. The selection of the baseline and Week 24 androstenedione values used to assess control for this endpoint is the same method as is used for the primary endpoint (and described in Section 6.3.3). The primary analysis of this endpoint will be performed using a CMH test as described in Section 9.2.2. The CMH test will compare treatment groups and will include the stratification factors used in the randomization. If the model fails to converge due to a small number of observations within a cell, stratification levels may be collapsed to allow for model convergence. Subjects whose androstenedione levels at Week 24 are not controlled will be considered non-responders. For subjects who are missing glucocorticoid dose, androstenedione, or both at Week 24, the multiply-imputed datasets from the primary endpoint will be used to determine response.

Descriptive statistics will be presented by treatment group for the number and percentage of subjects classified as responders and non-responders at each postbaseline visit. For the Week 24 visit, the treatment difference and p-value from the CMH analysis will also be displayed.

A tipping point sensitivity analysis of the achievement of reduction in physiologic glucocorticoid daily dose at Week 24 will be performed to assess the robustness of the missingness assumptions as was described for the primary endpoint in Section 9.3.3. The implementation procedure for the tipping point analysis is described in Appendix 16.6 for this key secondary efficacy endpoint.

A complete-case sensitivity analysis will also be performed to test the robustness of the multiple imputation procedure. The CMH analysis for the physiologic glucocorticoid daily dose endpoint will be repeated using only subjects with observed data at Week 24. Subjects who are missing the Week 24 secondary endpoint will be excluded from the analysis.

#### **9.4.3. HOMA-IR**

An additional key secondary endpoint is the change from baseline in HOMA-IR at Week 24 (in subjects without diabetes mellitus). HOMA-IR is calculated as: (fasting glucose in mmol/L x fasting insulin in mU/L) / 22.5. Subjects who are concomitantly taking insulin at Day 1 or subjects who are not fasting at the time of the assessment will be excluded from this analysis. The analysis of this endpoint will be performed using an ANCOVA model, as described in Section 9.2.1. Subjects who are missing HOMA-IR at Week 24 will have their data imputed through the multiple imputation procedure described in Section 16.2.

Statistical significance for the treatment comparison will be determined using the multiple comparison procedure described in Section 9.1. Descriptive statistics and LS means for change from baseline to Week 24 in HOMA-IR will be presented by treatment group along with the LS-mean treatment difference, 95% confidence intervals, and p-value.

A tipping point sensitivity analysis of change from baseline in HOMA-IR at Week 24 (in subjects without diabetes mellitus) will be performed to assess the robustness of the missingness assumptions as was described for the primary endpoint in Section 9.3.3. The implementation procedure for the tipping point analysis is described in Appendix 16.5 for each key secondary efficacy endpoint.

A complete-case sensitivity analysis will also be performed to test the robustness of the multiple imputation procedure. The ANCOVA analysis for the change from baseline in HOMA-IR at week 24 will be repeated using only subjects with observed data at Week 24. Subjects who are missing the Week 24 secondary endpoint will be excluded from the analysis.

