### 4.2. Key Secondary Efficacy – DB Period

Key secondary efficacy endpoints in the DB period are:

- change from baseline in serum androstenedione at Week 4
- achievement of a reduction in glucocorticoid daily dose to physiologic levels at Week 24
- change from baseline in homeostatic model assessment of insulin resistance (HOMA-IR; in fasting subjects not on insulin) at Week 24
- percent change from baseline in weight at Week 24
- change from baseline in percent total fat mass at Week 24

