#### **4.5. Exploratory Efficacy – OL Period**

Exploratory efficacy endpoints in the OL period include:

- percent change from baseline and OL baseline in glucocorticoid daily dose (in hydrocortisone equivalents adjusted for BSA [mg/m^2/day]) at Month 12, while Month 12 androstenedione values are adequately controlled at  $\leq 120\%$  of baseline or  $\leq$  ULN for age and sex
- achievement of a reduction in glucocorticoid daily dose to physiologic levels at Month 12
- change from baseline and OL baseline in hormone parameters (androstenedione, 17-OHP, ACTH, total testosterone, FSH, LH, progesterone, SHBG) at Month 12
- change from baseline and OL baseline in metabolic laboratory parameters (glucose tolerance [as measured by the post-GTT load glucose levels; in subjects without diabetes mellitus], HOMA-IR [in fasting subjects not on insulin], total cholesterol, LDL, HDL, HbA1c, triglyceride) at Month 12
- change and percent change from baseline and OL baseline in weight at Month 12
- change from baseline and OL baseline in BMI at Month 12

- change from baseline and OL baseline in waist circumference at Month 12
- change from baseline and OL baseline in percent total fat mass at Month 12
- change from baseline and OL baseline in total lean mass at Month 12
- change from baseline and OL baseline in total body mass (via DXA) at Month 12
- change from baseline and OL baseline in urine androgen metabolite levels at Month 12
- change from baseline and OL baseline in BMD at Month 12
- change from baseline and OL baseline in hirsutism (female subjects only) at Month 12
- change from baseline and OL baseline in acne (female subjects only) at Month 12
- change from baseline and OL baseline in bone markers (serum osteocalcin, serum bone-specific alkaline phosphatase, serum C-terminal telopeptide [CTX], urine N-terminal telopeptide [NTx]) at Month 12
- change from baseline and OL baseline in testicular adrenal rest tumor (TART) volume (expressed as a percentage of the total testicular volume) at Month 12 (male subjects only)
- change from baseline in menstrual regularity (premenopausal female subjects not using hormonal or IUD contraception only) at Month 12
- change in number of menstrual periods (premenopausal female subjects assigned to the placebo group for the DB period, not using hormonal or IUD contraception) at Week 24 to Month 12, compared to Day 1 to Week 24

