**Table 2: Evaluability of Subjects at Endpoint**

Subject Classification	Description
Completers	Subjects in the FAS who completed through the time of the endpoint (Week 4 or Week 24, as applicable) on study drug and have an evaluable measurement for that endpoint. For endpoints with more than one data component, the subject must have complete data for all components of the endpoint.
Retrieved Dropouts	Subjects in the FAS who discontinue study drug prior to the time of the endpoint collection but remain in the study and have an evaluable measurement for that endpoint. For endpoints with more than one data component, the subject must have complete data for all components of the endpoint.
Non-retrieved Dropouts	Non-retrieved dropouts are subjects in the FAS who discontinue from the study and from study drug and do not have an evaluable measurement for that endpoint.
On Drug-Missing Endpoint	Subjects in the FAS who are on study drug at the time of the endpoint but do not have an evaluable measurement for that endpoint.

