### **10.3. Metabolic Assessments**

Descriptive statistics will be presented by treatment group and visit for the observed and change from OL baseline values for the following metabolic assessments: HOMA-IR (in subjects not taking insulin and fasting), glucose tolerance (as measured by the post-GTT load glucose levels), fasting lipid panel (including total cholesterol, LDL, triglycerides, and HDL), and HbA1c (stratified by subjects with and without diabetes mellitus). Percent change from baseline will also be summarized for all parameters except HbA1c.

The above summaries will be repeated for the change from baseline (Day 1) to Month 12 in each of the metabolic assessments.

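### SAP Sections 4.2 and 9.4.3 give different populations for the alpha-controlled HOMA-IR endpoint, and the fasting exclusion in 9.4.3 names no visit

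*SAP*

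**What the plan says.** SAP Section 4.2 lists the key secondary endpoint as "HOMA-IR; in fasting subjects not on insulin) at Week 24". SAP Section 9.4.3, which specifies its analysis, says "An additional key secondary endpoint is the change from baseline in HOMA-IR at Week 24 (in subjects without diabetes mellitus") and repeats the restriction for the sensitivity analysis: "A tipping point sensitivity analysis of change from baseline in HOMA-IR at Week 24 (in subjects without diabetes mellitus"). It then adds that "Subjects who are concomitantly taking insulin at Day 1 or subjects who are not fasting at the time of the assessment will be excluded". It does not say how diabetes is determined. Day 1 criteria for diabetes (medical history, glucose tolerance test or HbA1c) are written out in SAP Section 9.5.3 for the glucose tolerance endpoint, but 9.4.3 does not refer to them.

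On missing data, 9.4.3 says "Subjects who are missing HOMA-IR at Week 24 will have their data imputed through the multiple imputation procedure described in Section 16.2". SAP Table 2 has a class for subjects "on study drug at the time of the endpoint but do not have an evaluable measurement for that endpoint", and step 1 of Section 16.2 imputes such subjects from their own treatment group.

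Protocol Section 13.6.1.3 analyses HOMA-IR in the FAS and states no restriction by diabetes, insulin or fasting. SAP Section 13 says that its list of deviations is complete. The only item in it is the change to the safety analysis set.

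**The concern.** A confirmatory endpoint needs one analysed population, fixed in advance and described the same way wherever it is defined. Here two sections of one SAP select different subjects for a Holm-tested endpoint. If the programmer follows 9.4.3, the endpoint definition in 4.2 does not describe the subjects analysed, and a restriction absent from the protocol enters without being declared. If the programmer follows 4.2, the analysis departs from 9.4.3. A choice between them that is still open at unblinding could be made with the results in view.

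The fasting sentence raises a different issue. A restriction fixed at Day 1 leaves the randomised comparison intact, because the first dose is taken that evening. Excluding subjects for their fasting status at Week 24 is a post-randomisation exclusion and may not leave it intact. The SAP already has an imputation route for such subjects and does not say which route applies.

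**Working it through.** The main check compares texts. I applied each section to five kinds of subject:

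| Subject | SAP 4.2 | SAP 9.4.3 |
|---|---|---|
| No diabetes, no insulin, fasting at both visits | in | in |
| Diabetes, no insulin, fasting at both visits | in | out |
| On insulin at Day 1 | out | out |
| No diabetes or insulin at Day 1, insulin started later | not stated (no visit given) | in, if diabetes is judged at Day 1 |
| No diabetes, no insulin, not fasting at Week 24 | not stated | dropped, or missing and imputed |

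The second row is the direct disagreement.

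*Could the two phrases mean the same thing?* No. One bullet in SAP Section 4.5 restricts glucose tolerance to subjects without diabetes and gives a different rule for insulin resistance: "HOMA-IR [in fasting subjects not on insulin". Sections 4.2 and 4.3 make the same split. Section 10.3 again has "HOMA-IR (in subjects not taking insulin and fasting".

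*Could the second row be empty by design?* No. Diabetes is not itself listed as an exclusion criterion, Protocol Section 9.9.2 gives subjects with diabetes their own dosing instruction, and SAP Section 7.4.1 lists diabetes among the conditions to be summarised at entry.

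*Does the plan give a size for this endpoint?* No. The only power statement is for the primary endpoint: above 90% at effect size 0.55 with 110 and 55 subjects. It reproduces (91.5% by the normal approximation, 91.2% by the noncentral t), but it says nothing about HOMA-IR. The documents give no rate of diabetes, insulin use or non-fasting, so the number of subjects affected cannot be computed. Two illustrations show the order of magnitude.

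*Diabetes restriction.* Let a share q of subjects have diabetes without insulin, and let their treatment effect differ by g SD from that of the others. The effect with them included is (1 − q)d + q(d + g) = d + qg, so the two populations differ by qg. Assuming q = 5% to 10% and g = 0 to 0.5 SD:

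- lowest: 0.05 × 0 = 0 SD;
- highest: 0.10 × 0.5 = 0.05 SD.

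The unadjusted standard error with 110 and 55 subjects is √(1/110 + 1/55) = 0.165 SD, so the top of the range is 0.05 / 0.165 = 0.30 standard errors. The standard error also grows by 1/√(1 − q): a factor of 1.026 at q = 5% and 1.054 at q = 10%.

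*Fasting at Week 24, subject still on drug.* I compared excluding such subjects with imputing them from their own arm. The simulation had 110 versus 55 subjects, baseline and sex in both the ANCOVA and the imputation model, Rubin's rules, 1,500 trials and 30 imputations. With 6 of 110 affected and an assumed effect of −0.5 SD, exclusion gave −0.501 (SE 0.1600) and imputation gave −0.501 (SE 0.1602). For these subjects the choice hardly changes the result. It could matter more for off-drug crinecerfont subjects if they were imputed from placebo, but Section 16.2 uses placebo donors only when retrieved dropouts are too few.

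**The case against.** The strongest reply is that 9.4.3 is the operative text. A programmer would apply its criteria together (no diabetes, no insulin at Day 1, fasting), 4.2 is a shorter label, and 9.5.3 holds the only written diabetes criteria, so what is missing is a cross-reference. This is fair as a prediction of what would be programmed. It does not remove the disagreement: 4.2 would still misdescribe a tested endpoint, and Section 13 would still be incomplete.

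On fasting, a reader might infer that 9.4.3 contradicts the imputation rules. The documents do not support that. HOMA-IR is computed from fasting glucose and fasting insulin, so a non-fasting sample gives no valid value and can naturally be treated as not evaluable and imputed. Protocol Section 9.9.2 requires a fast of at least 8 hours at Day 1 and Week 24, so such samples should be few. What stands is that the sentence speaks of excluding subjects, names Day 1 for insulin and names no visit for fasting.

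Two further limits are accepted. Sections 4.5 and 10.3 concern descriptive open-label summaries on a different analysis set, without alpha. They show how the SAP uses its terms, and they are not a second conflict. Nor does analysis in the FAS rule out an endpoint-specific subset: Protocol Section 13.6.1.4 restricts glucose tolerance to subjects without diabetes within the FAS. The narrower point is that the protocol states that subset for glucose tolerance and none for HOMA-IR.

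**Conclusion.** The point holds in two parts of unequal strength. The difference between 4.2 and 9.4.3 over diabetes is an inconsistency on the face of the SAP, for an alpha-controlled endpoint, and nothing in either document reconciles it. The missing visit in the fasting exclusion is an ambiguity, with one reading that drops subjects after randomisation and one that does not.

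The size is unknown and probably small. The range of 0 to 0.05 SD for the diabetes restriction rests wholly on assumed values of q and g, and the simulation on assumed counts and an assumed effect. Neither predicts this trial. A reader might go further and infer that the HOMA-IR result will be biased or its type I error inflated. The documents do not show that: either population, if fixed on Day 1 status, gives a valid randomised comparison. The case for acting is that the population of a tested endpoint should be settled before unblinding, and settling it is cheap. This should be corrected, but it does not threaten the trial's main conclusion.

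**What to change.** Before unblinding:

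1. Put one identical population statement in Sections 4.2 and 9.4.3. Base every criterion (insulin use, fasting and, if kept, diabetes) on Day 1 status only, and state all of them in both places. If the diabetes restriction is kept, define it by reference to the Day 1 criteria in 9.5.3.
2. State that a non-fasting Week 24 sample is a missing HOMA-IR value, imputed under Section 16.2, and not a reason to exclude the subject.
3. List the restriction, relative to Protocol Section 13.6.1.3, in SAP Section 13.

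The cost is wording in three SAP sections and one derivation flag. No new data are needed.
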